Figure 3. In a proof of concept study, VO_2 monitoring of rabbits (weight ~3 kg) undergoing a 30 minute period of observation, followed by a 15 minute period of asphyxia, then a post-asphyxial recovery. Exemplary VO_2 tracings shown of animals treated (blue line) and untreated (red line) with an intravenous formulation of oxygen which prevented severe hypoxemic-ischemic injury. Animals which suffered severe injury exhibited a significant decrement in VO_2 early during the recovery period, a pattern which worsened prior to post-asphyxial loss of circulation. Animals who experienced treated asphyxial injury had an unchanged VO_2 curve. **A central hypothesis of this study is therefore whether VO_2 may represent a sensitive, real-time, prospective, and non-invasive marker of circulatory failure and inadequate DO_2 in newborns at risk for this life-threatening problem.**

measurements, intermittent measurements of lactate and superior vena cava saturations) add power in predicting which patients will experience PLOC.

Hypothesis: Continuous measurements of VO₂ and SVC saturations will add significantly to our ability to predict which patients will undergo PLOC.

Study Design

We will prospectively and continuously measure VO₂ and SVC saturations in newborns undergoing stage I palliation (S1P) or hybrid palliation (HP) for HLHS (n=20) or arterial switch operation (ASO) for d-TGA/IVS (n=20), beginning at the time of first preoperative intubation and ending at the time of the first postoperative extubation. Newborns will be followed for the occurrence of PLOC as the primary endpoint. A study schematic is attached as **Appendix 1**.

Study Population

Inclusion criteria.

1. Patient from birth to 6 months of age
2. HLHS AND no prior operations AND planned S1P or HP
OR
d-TGA/IVS AND planned ASO
3. Written parental informed consent

Exclusion criteria.

1. Weight < 2 kg
2. Disease specific
 - A. HLHS patients: Infants whose surgical plan includes a neonatal biventricular repair will be excluded.
 - B. d-TGA/IVS patients: Newborns with any additional cardiac defect other than an atrial septal defect will be excluded.
3. Patients on ECMO preoperatively
4. Clinically significant tracheo-esophageal fistula or known preoperative air leak

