Data Management and Statistical Analysis

Data management methods

Upon entry into the study, each patient will be assigned a unique patient identifier which is unique from their medical record number for the purpose of patient tracking. A spreadsheet which links each patient's UPI and BCH medical record number will be

kept in a separate binder, locked in the PI's office. The UPI will be used to identify patients on all study-related materials, including the laptop used to collect data from the GE monitor (which includes all ventilation parameters and SVC measurements), and on the data collection forms. Data from the T3 system will be extracted from SQL T3 database, and stored in a deidentified manner using the same UPI.

Logistic considerations

At the time of study enrollment, baseline characteristics will be collected and recorded on a deidentified form. At the time of first intubation or CVL placement, the pole-mounted GE monitor will be brought to the room by study personnel, and data recording will begin in realtime to the S5 Collect program using an attached laptop (**Figure 6**). The program file will be saved as the patients UPI and will not contain confidential information. Care will be taken to synchronize the time stamps within each of the devices in order to ensure proper alignment of the various data sources.

Each day, a member of the study team will visit the patient's bedside to abstract the relevant information from the medical record, with corroboration from the patient's bedside nurse and treating team. When needed, the patient's cardiac anesthesiologist or perfusionist will be contacted to clarify.

Using a study laptop, all requisite information will be entered into a Microsoft Excel spreadsheet with the desired values listed on the left and each hour listed across the right. Data will be hand-entered into the spreadsheet by a member of the research team, and annotated as necessary to clarify discussions with relevant parties. These data will be double checked by a second member of the study team within 7 days.

Quality control methods

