Quality in the data collected by the oxygen consumption monitor will be ensured by a self-test at startup according to the manufacturer's instructions. Further, anesthesiologist and respiratory care staff will be instructed to monitor for the degree of air leak from the respiratory system by calculating the difference between inspiratory and expiratory measured tidal volumes. If the airleak exceeds this value, air may be added to the tracheal tube cuff. We have shown that when this difference is <15%, VO_2 data are accurately measured in newborns.²⁴ Further, an absence of end-tidal CO_2 data will be used as a signal of an endotracheal tube disconnection and possible suctioning event. VO_2 measurements are known to be unstable for several minutes following suctioning²⁸, so we will exclude VO_2 data for 10 minutes following any ETT disconnect from analyses.

Figure 6. The oxygen-based monitoring and data collection systems utilized for this study are attached to a rolling pole which can be placed anywhere around the patient and easily moved for convenience and safety.

Data within the SVC monitoring probe will be ensured by an in vitro calibration prior to probe insertion. When ever the treating team sends a venous blood gas from the central venous line, the co-oximetry value will be entered into the machine and used to recalibrate the probe in real-time.

Quality in the transfer of data from the medical record to the spreadsheet will be ensured by an independent review of the primary data by a second member of the study team. Furthermore, when possible, the fields for data entry will contain 'Data Validation' functions (i.e. value will turn red if outside expected limits, and hard stops will be inserted for physiologically impossible values). Additionally, drop down lists will be utilized when possible to minimize data entry errors.

Data Analysis Plan

Patients will be divided into patients who do and do not experience PLOC. All variables will be normalized to hours prior to bypass, bypass time and hours post-bypass time, such that all data for a specific post-bypass time will be aligned between patients. All weight-dependent variables will be normalized to preoperative body weight. Using GraphPad Prism, each variable will be entered into a different column for analysis.

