Simple analyses (e.g. mean, standard deviation, tests for normality) will be completed within GraphPad. With regards to the primary endpoint, VO₂ measurements will be analyzed for 120 minutes prior to a PLOC event in cases, and a randomly selected 120 minute period in controls. Values will be compared between cases and controls using generalized estimating equations (GEEs) to account for the correlation of multiple measurements within the same patient and to compare means between cases and controls. A post-hoc broken stick analysis will be used to determine the time prior to the event at which the VO₂ changed in each patient experiencing an event. Data for HLHS and dTGA patients will be pooled together.

More complex analyses will be completed by a collaborating company called Etiometry (including [name] and [name], co-investigators on this study), with whom the PI and others within the CICU have an established relationship. Deidentified information will be sent to the company, who will complete further analyses.

Power Calculations and Sample Size

The measured oxygen consumption in neonates following S1P has been described as 86 ± 16 mL/min/m^{2.22}. A sample size that includes 3 cardiac arrest events would allow us to detect a true decrease of 53 mL/min/m² in oxygen consumption with 90% power and a significance level of 0.05 (two tailed). Based on the significant change in VO₂ noted in the animal studies preceding cardiac arrest, we do not feel that this number is an unreasonable number. In order to collect 3 patients meeting the endpoint, we predict that we will require 20 patients undergoing S1P.

Risks and Discomforts

Because this is a prospective, observational study which we do not expect to change the standard of care, the risks associated with this study are really those of the standard

of care. The VO_2 measurements will be taken using an FDA-approved device which samples gas from the side of the tracheal tube of each patient. In reality, the adapter used by the study monitor is smaller and lighter than than used in our current capnographs, so the risk of accidental endotracheal tube removal should be the same or lower.

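### Neither the case window nor the control window for VO₂ is confined to time after separation from bypass, so an early PLOC can bring bypass or weaning minutes into the primary comparison

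*Combined protocol and SAP*

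**What the plan says.** The Data Analysis Plan defines the primary comparison by two windows. For cases, VO₂ is analysed "for 120 minutes prior to a PLOC event in cases". For controls, "a randomly selected 120 minute period in controls". The two are compared with GEE, and a post-hoc broken-stick analysis then dates the VO₂ change in each infant with an event.

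Study Design has measurement "beginning at the time of first preoperative intubation and ending at the time of the first postoperative extubation". Logistic considerations says that when the first tube or central line is placed, "data recording will begin in realtime to the S5 Collect program using an attached laptop". The Appendix 1 schematic starts VO₂ collection under the operating-room step. Planned recording therefore runs through the operation.

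The Data Analysis Plan also sets the time axis: "All variables will be normalized to hours prior to bypass, bypass time and hours post-bypass time". Bypass is thus identified as a phase, but no sentence removes it from the primary comparison.

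The only stated VO₂ exclusion is under Quality control methods. Absent end-tidal CO₂ signals a tube disconnection, and the plan drops VO₂ "data for 10 minutes following any ETT disconnect from analyses".

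**The concern.** The Oxygen consumption section explains that VO₂ is derived from inspired and expired airway gas. It therefore measures uptake through the lungs only. While the pump does all or part of the gas exchange, a recorded airway VO₂ understates what the infant consumes.

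The case window is a fixed 120 minutes counted back from PLOC, and PLOC is defined without a minimum time after surgery. Followed as written, a PLOC less than 120 minutes after separation pulls bypass or weaning minutes into the window. Any low values there would push the case mean down, which is the direction of the Aim 2 hypothesis. With about 3 cases expected, one such infant is a third of the case group. The broken-stick fit works infant by infant, so it could date the end of bypass rather than a physiological change.

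The control window has the same gap. It can fall before bypass, when it describes a preoperative infant, or during bypass, when its values are no more valid than a case's.

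**Working it through.** The plan gives no figure for this point. Its power statement and background supply the inputs.

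**Inputs from the documents**
- Reference VO₂ after S1P: mean 86, SD 16 mL/min/m² (Power Calculations and Sample Size).
- Events: 3 planned among 20 S1P infants. The 10–15% PLOC rate in the HLHS background section gives 20 × 0.10 = 2 to 20 × 0.15 = 3, so 3 is the top of the plan's own range.
- Window: 120 minutes.

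**Assumptions, because the documents are silent**
- t, the minutes from separation to PLOC.
- r, the VO₂ recorded on bypass: 0 or 43 (half of 86).
- One early case among 3, with bypass values recorded and kept.

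**Step 1. Share of the case window on bypass:** (120 − t)/120 for t below 120, otherwise 0.

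**Step 2. Fall in that infant's mean:** (86 − r) × share.

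**Step 3. Fall in the case-group mean:** the Step 2 result divided by 3.

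| t (min) | Share | Infant's fall, r = 0 | Case-mean fall, r = 0 | Infant's fall, r = 43 | Case-mean fall, r = 43 |
|---|---|---|---|---|---|
| 120 or more | 0 | 0 | 0 | 0 | 0 |
| 90 | 0.25 | 21.5 | 7.2 | 10.8 | 3.6 |
| 60 | 0.50 | 43.0 | 14.3 | 21.5 | 7.2 |

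At t = 60 and r = 0, the shift is 14.3/16 = 0.9 SD.

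**Step 4. Only a wean is retained.** Suppose the unventilated span is removed and 15 minutes of shared gas exchange at half the true VO₂ remain: 86 × 0.5 × 15/120 = 5.4 for that infant, and 5.4/3 = 1.8 on the case mean (0.1 SD). If the 10-minute exclusion also removes the first 10 of those minutes, 5 remain: 86 × 0.5 × 5/120 / 3 = 0.6.

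**Step 5. Bypass values are blank or removed.** The shift is 0. The case window is then shorter than 120 minutes, and the plan has no rule for that.

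**Step 6. Controls.** For R hours of recording and B minutes of bypass, a random 120-minute window touches bypass with probability about (B + 120)/(60R − 120). With R of 48 to 120 and B of 90 to 150 (assumed), this runs from 210/7,080 = 3% to 270/2,760 = 10%. A case with PLOC inside 120 minutes always has a window that reaches back past separation, so the two sides need not cancel.

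**The case against.** The strongest reply is that the exposure is narrow and the plan already removes most of it.

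- **Setting.** PLOC is a postoperative event. Its rate is quoted for the CICU, and Appendix 1 collects the primary outcome there. For bypass to enter the window, an infant must come off bypass, reach the unit and arrest within two hours. This stands, and it makes a PLOC at 30 minutes or so remote. It does not rule out one at 60 to 120 minutes.
- **Low bypass VO₂ is assumed.** The value is calculated breath by breath, so without ventilation the monitor may record nothing. This also stands. The documents do not say whether the lungs are ventilated on bypass or what is recorded.
- **The end-tidal CO₂ rule.** Its natural reading drops the flagged span as well as the 10 minutes after it, and near-zero VO₂ is most plausible when CO₂ is absent. This largely stands. The literal wording covers only the minutes after a disconnect, and under either reading a ventilated wean with CO₂ present is not flagged. That remainder is worth about 2 mL/min/m² or less on the case mean.
- **Bypass is already labelled.** True, but a label is not an exclusion.

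A reader might infer that the primary result will be inflated by false low VO₂. Simulating 3 cases against 37 controls with no true effect, and a t-test on infant means standing in for GEE, a nominal 5% test rejects about a quarter of the time when one case has PLOC at 60 minutes and bypass VO₂ of 0. That figure is conditional on an early case and on zeros being recorded and kept. If instead 10% of PLOCs (assumed) fall evenly between 60 and 120 minutes, still with zeros kept, rejection is about 7%. The documents establish none of these conditions.

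**Conclusion.** The gap in the text is real: both windows are open to time before separation from bypass, and no rule closes them. It is more than missing detail, because the stated rule, applied as written, can admit VO₂ that does not measure the infant's consumption.

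The effect on the case mean depends on facts that the documents do not give:
- zero for a PLOC at 120 minutes or later, or if bypass values are blank or removed;
- about 2 mL/min/m² if one of 3 cases retains only a 15-minute shared wean;
- up to about 14 mL/min/m² if one case has PLOC at 60 minutes and near-zero bypass values are recorded and kept.

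The documents do not support saying that bias will occur, how often, or that it arises only on the case side. The point merits a change because the case group is very small and the correction is nearly free.

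**What to change.** Add to the Data Analysis Plan, before any data are analysed:
- Only VO₂ recorded after final separation from bypass enters the primary comparison and the broken-stick fit.
- The case window is the 120 minutes before PLOC or the time since final separation, whichever is shorter.
- Each control window has the same length as a case window and lies at the same post-bypass time.
- The length of every window shorter than 120 minutes is reported.

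The cost is a few lines of analysis wording. Bypass is already a phase of the time axis, and pump times are collected under Operative characteristics. The downside is that an early case contributes a shorter window and a less precise mean. Reporting that length is preferable to a fixed minimum, which could discard one of about three cases.

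### The primary VO2 contrast sets a window tied to a postoperative event against a random control window with no stated timing rule, and pools two diagnoses without a diagnosis term

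*Combined protocol and SAP*

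**What the plan says.** The Data Analysis Plan divides patients into those with and without PLOC. Cases contribute VO2 from the 120 minutes before the event; the comparison is "a randomly selected 120 minute period in controls". Means are compared by generalized estimating equations (GEE), with no covariate named. The same paragraph adds: "Data for HLHS and dTGA patients will be pooled together".

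Four other statements bear on this:

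- Specific Aim 2 defines PLOC as a postoperative event.
- Study Design has recording "beginning at the time of first preoperative intubation and ending at the time of the first postoperative extubation". Logistic considerations says: "At the time of first intubation or CVL placement, the pole-mounted GE monitor will be brought to the room by study personnel".
- The Data Analysis Plan also says: "All variables will be normalized to hours prior to bypass, bypass time and hours post-bypass time". Pre-bypass time is therefore part of the analysis data.
- Power Calculations and Sample Size says: "In order to collect 3 patients meeting the endpoint, we predict that we will require 20 patients undergoing S1P". No event rate is given for d-TGA.

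**The concern.** A case window is fixed by an event that can happen only after surgery. A control window is fixed by a random draw whose sampling frame is not defined. The protocol itself says that VO2 moves with fever, activity and inotropes (Background, The Importance of Oxygen Delivery) and with sedation and paralysis (Endpoints/Outcomes, Treatments). These change over the perioperative course, so windows from different times can differ in VO2 for reasons unrelated to an approaching arrest.

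Diagnosis raises the same difficulty. If the events fall where the sample-size section expects them, all cases have HLHS and about half of the controls have d-TGA. Any difference in VO2 between the diagnoses then enters the case-control contrast. At stake is whether a lower VO2 in cases can be read as a warning of PLOC. With about three events, the definition of the control largely decides that.

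**Working it through.** **Inputs.** From the documents: 20 HLHS and 20 d-TGA patients (Study Design); 3 events, SD 16 and a detectable decrease of 53 mL/min/m² at 90% power, two-sided 0.05 (Power Calculations and Sample Size). Assumed: a VO2 gap between diagnoses of 0, 10 or 20; an event split of 3/0 or 2/1 (HLHS/d-TGA); one window mean per patient with SD 16.

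**The plan's own figure.** The plan names neither the test nor the number of controls behind 53. A two-sided t-test at 90% power detects 57.4 with 3 v 3 patients, 34.4 with 3 v 17 and 32.0 with 3 v 37; a normal approximation with 3 v 3 gives 42.3. None returns 53, so it serves below only as a yardstick.

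**Timing.** If a fraction f of control windows lies in a phase where VO2 differs by T, the contrast is biased by f × T. The documents give neither quantity, so no figure is offered. A diagnosis term does not remove this bias.

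**Diagnosis: bias.** Bias = gap × (d-TGA share of controls − d-TGA share of cases).

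- 3/0 split: 20/37 − 0 = 0.541, so 5.4 at a gap of 10 and 10.8 at 20.
- 2/1 split: 19/37 − 1/3 = 0.180, so 1.8 and 3.6.

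If d-TGA VO2 is the higher, cases look falsely low; if it is the lower, a true fall is masked.

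**Diagnosis: type I error.** Simulation of 40 normally distributed patient means with no PLOC effect (200,000 runs):

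| Patient-level t-test | gap 0 | gap 10 | gap 20 |
|---|---|---|---|
| 3/0, pooled | 5.0% | 7.2% | 11.7% |
| 3/0, diagnosis term | 5.0% | 5.0% | 5.0% |
| 2/1, pooled | 5.0% | 4.3% | 2.9% |

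**A separate effect: few case clusters.** If the GEE uses an uncorrected robust variance and a normal reference (the plan specifies neither), type I error at a gap of 0 is already 20.7% pooled and 17.8% with the diagnosis term. That comes from having 3 case clusters, not from confounding.

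**Precision.** The detectable difference d solves 90% power in a noncentral t with noncentrality d/(16√v).

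- Pooled: v = 1/3 + 1/37 = 0.360, 38 df, d = 32.0.
- Diagnosis term, 3/0: v = 1/3 + 1/17 = 0.392, 37 df, d = 33.4.
- Time matching plus diagnosis term, 3 HLHS cases, h HLHS and k d-TGA controls: v = 1/3 + 1/h, with h + k df. The d-TGA controls add only degrees of freedom.

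| h + k | v | df | d |
|---|---|---|---|
| 5 + 5 | 0.533 | 10 | 42.1 |
| 4 + 1 | 0.583 | 5 | 50.0 |
| 3 + 3 | 0.667 | 6 | 51.1 |
| 2 + 4 | 0.833 | 6 | 57.1 |

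Five controls (4 + 1) can thus do better than six (2 + 4): the HLHS count governs.

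**Permutation limit.** With 3 HLHS cases and 3 HLHS controls, a test stratified by diagnosis has C(6,3) = 20 arrangements, so its smallest two-sided p is 2/20 = 0.10. It could not reject at 0.05 whatever the effect.

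**The case against.** The strongest reply is that a postoperative control window is plainly meant. PLOC is postoperative by definition, the analysis section aligns data by post-bypass time, and the Appendix 1 schematic lists the start of data collection under the cardiac operating room, so many patients may have little pre-bypass recording. That weakens the timing point. It does not remove it: the alignment indexes the data and is not tied to how a control window is chosen, and a postoperative limit alone would still leave the post-bypass hour unmatched. A reader might infer that the plan intends preoperative control windows. Nothing in the documents says so; the rule is simply not set.

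On diagnosis, pooling is an open choice. The gap and the 3/0 split are both assumed, and the bias stays well below 53. All of that stands. A reader might go further and conclude that pooling would by itself produce a positive result. The figures do not support that: the bias is modest, and at 2/1 the pooled t-test is not inflated. Nor should the high GEE error rates be blamed on pooling, since most of the excess is there with no gap at all.

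Finally, the plan includes a within-patient check: "A post-hoc broken stick analysis will be used to determine the time prior to the event". Diagnosis cannot confound a comparison inside one patient, and the analysis is written into the plan. It uses cases only and is not the primary contrast, so it mitigates in part.

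**Conclusion.** The concern holds as a gap in the specification of the primary contrast that is cheap to close. As written, the plan allows perioperative phase and diagnosis to enter the case-control difference in VO2, in either direction. The size is unknown: the documents give no d-TGA VO2, no d-TGA event rate and no VO2 time course. Under an assumed gap of 10 to 20 mL/min/m² with all three events in HLHS patients, the bias is 5.4 to 10.8 and a patient-level t-test has a type I error of about 7 to 12% in place of 5%. These figures illustrate and do not predict. They rest on SD 16, normal patient means and exactly three events. Confidence is medium.

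**What to change.** 1. Restrict control windows to postoperative monitored time. For each event, take the 120-minute window at the same post-bypass hour, or within a pre-stated hour band, from all patients still monitored and event-free then. A patient may supply several windows, so average them or cluster them by patient. State whether a patient who later has PLOC may serve as a control.
2. Add a diagnosis term to the primary model, keep any d-TGA event, and report an HLHS-only sensitivity analysis.
3. Separately, take the p-value from a patient-level regression with a t reference, because the diagnosis term does not repair the few-cluster problem. Do not rely on a diagnosis-stratified permutation test when few HLHS controls remain.
4. Base any widening of the hour band on the number of HLHS controls, not on the total.

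The cost is plan wording and programming, since time stamps and diagnoses are already collected. The downside is precision: the detectable difference goes from 32.0 to 33.4 with the diagnosis term alone, to about 42 with 5 + 5 time-matched controls, and past 53 with 2 + 4. Those control numbers are assumed, because the documents give no extubation times, and the figures take one window per control.

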In the BCH CICU, approximately 10-15% of neonates undergoing a stage I palliation (S1P) experience PLOC and receive some resuscitation, often times in the form of extracorporeal membrane oxygen (EMCO) device support. These patients often experience increased ICU and hospital lengths of stay, higher hospital morbidity and mortality, and worse neurologic outcomes.⁴⁻⁶ The purpose of this study is to determine whether continuous monitoring of VO_2 and SVC saturations will allow development of signs to predict which patients are at highest likelihood of experiencing a PLOC before the event, permitting time for interventions to take place prior to an injurious or potentially lethal event.

[figure not shown]

Figure 2. In patients born with an inadequate left ventricle, the right ventricle is used to pump blood to both the body and the lungs simultaneously and in parallel by connecting the pulmonary artery to the small aorta, and creating a shunt from this circulation to the lungs. This circulation leads to increased oxygen demand for the heart. When this demand is not met, myocardial dysfunction and PLOC result. Figure from Ohye, *NEJM*, 2010. {Ohye:2010kn}

Currently Used Markers of Oxygen Delivery

Assessing the physiologic state of patients is a complex but vitally important task. At the bedside, the clinician combines many pieces of data to assess the adequacy of end organ oxygen delivery, each of which has strengths and weakness as a clinical sign. Basic hemodynamic parameters (aka vital signs) include a patient's heart rate, arterial and venous blood pressures, oxygen saturations and temperature are central to the assessment of a patient's physiologic state, and are often the most important clues to inadequate oxygen delivery. Further to this includes markers of end organ function, such as urine output, coagulation parameter, as well as laboratory indices of hepatic and renal function add some degree of confidence that our general assessments are correct.

In patients at higher risk of insufficient DO_2 , advanced monitoring techniques are commonly used. The three most commonly used techniques in routine use in neonates undergoing congenital heart surgery include (1) cerebral near infrared spectroscopy (cNIRS), (2) SVC saturation sampling, and (3) serum lactate measurements.

Cerebral NIRS

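### The primary GEE comparison rests on about 3 case patients, but the plan fixes no working correlation, variance estimator, reference distribution or small-sample correction, and the real error of the 5% test depends on them

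*Combined protocol and SAP*

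**What the plan says.** The Data Analysis Plan takes VO₂ over the 120 minutes before the event in cases and over a random 120-minute period in controls. It then states: "Values will be compared between cases and controls using generalized estimating equations (GEEs"), giving as reasons the within-patient correlation and the wish "to compare means between cases and controls". It adds: "Data for HLHS and dTGA patients will be pooled together".

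Power Calculations and Sample Size gives VO₂ as 86 ± 16 mL/min/m² and says: "A sample size that includes 3 cardiac arrest events would allow us to detect a true decrease of 53" mL/min/m² "with 90% power and a significance level of 0.05 (two tailed"). It continues: "In order to collect 3 patients meeting the endpoint, we predict that we will require 20 patients undergoing S1P". The section on HLHS and the risk of PLOC gives the rate behind this: "approximately 10-15% of neonates undergoing a stage I palliation (S1P) experience PLOC". Study Design adds a second group of 20, "arterial switch operation (ASO) for d-TGA/IVS (n=20").

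No section names a working correlation, variance estimator, reference distribution or small-sample correction for the GEE. GraphPad is named for simple analyses. More complex analyses go to a collaborating company, with no method stated.

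**The concern.** GEE deals with correlation among readings within a patient. It does not add patients. At one reading per second a 120-minute window can hold 120 × 60 = 7,200 values, yet only about three patients inform the case-side variance.

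The robust (sandwich) variance usually paired with GEE relies on many clusters in each group. With three it is too small on average and very unstable. A model-based variance avoids that, but borrows the control spread for the cases, which is safe only if the two spreads are equal. The documents give one SD, from S1P neonates, and do not address this.

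This is the only test named for the primary VO₂ comparison, so at stake is whether its p-value and interval mean what the stated 5% level says. Because the choice is open, it could also be made after the data are seen. Patient care is not at stake: VO₂ is recorded but hidden from clinicians, and discontinuation of the research depends on adverse events.

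**Working it through.** **Inputs.** From the sample-size section: 3 events, SD 16, decrease 53, power 90%, two-sided 0.05. From Study Design and the pooling sentence: 20 + 20 = 40 patients, so 3 v 37 if no ASO patient has an event (an assumption; no ASO rate is given). Using only the 20 HLHS patients, the layout is 3 v 17.

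**The plan's own figure.** (t₀.₉₇₅,₄ + z₀.₉₀) × SD × √(2/3) = (2.776 + 1.282) × 16 × 0.8165 = 53.0. The stated 53 is thus reproduced by a 3 v 3 patient-level comparison with a 4-df t critical value. This is a reconstruction; the plan shows no formula. If right, the sizing used a small-sample reference that the GEE text does not carry over.

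**Why the uncorrected robust variance is too small.** With equal reading counts, the GEE group effect is the difference of patient means. Its true variance is SD²(1/n₁ + 1/n₀). The robust variance is (sum of squares)/n² per group, so its expectation is SD²[(n₁−1)/n₁² + (n₀−1)/n₀²].

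- 3 v 37: true 256 × (0.3333 + 0.0270) = 92.3; expected robust 256 × (0.2222 + 0.0263) = 63.6; ratio 0.69.
- 3 v 17: true 256 × (0.3333 + 0.0588) = 100.4; expected robust 256 × (0.2222 + 0.0554) = 71.1; ratio 0.71.

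In 3 v 37 the case side supplies 0.3333/0.3604 = 92% of the true variance, estimated on 2 df. That instability raises the error further.

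**True error of a nominal 5% test** (equal means, normal patient means, 400,000 simulated data sets per setting):

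| Method | Case SD / control SD | 3 v 17 | 3 v 37 |
|---|---|---|---|
| Robust, normal reference | 0.5 | 12% | 15% |
| | 1 | 18% | 21% |
| | 2 | 22% | 24% |
| Robust, t on N−2 df | 1 | 15% | 19% |
| Exchangeable model-based, normal reference | 0.5 | under 1% | under 1% |
| | 1 | 6.5-7.9% | 5.7-6.4% |
| | 2 | 25-28% | 29-30% |
| Exchangeable model-based, t on N−2 df | 1 | 5.0% | 5.0% |
| | 2 | 22% | 27% |
| Kauermann-Carroll variance, fixed Satterthwaite df | 0.5 | 1.0% | 1.0% |
| | 1 | 3.0% | 3.2% |
| | 2 | 5.7% | 5.2% |

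The model-based ranges cover variance divisors N−2 and N. Other corrected versions at equal SD fall in between: Kauermann-Carroll with a normal reference 13-16%, Mancl-DeRouen with a normal reference 10-12%, and Kauermann-Carroll with data-estimated Satterthwaite df 7-8%.

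The fixed df are (1/n₁ + 1/n₀)² / [(1/n₁)²/(n₁−1) + (1/n₀)²/(n₀−1)] = 2.76 for 3 v 17 and 2.34 for 3 v 37.

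**Check on fitted GEEs.** Exchangeable fits with 12 or 24 readings per patient gave 16-22% for robust and 6-8% for model-based. Model-based variance with an independence working correlation gave over 40% (about 50% at 3 v 17 with 12 readings), under an assumed intraclass correlation of 0.6.

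**Other event counts** (equal SD). Robust with a normal reference: 28.5% at 2 v 18, then about 15%, 13% and 11% with 4, 5 and 6 events of 40. The fixed-df test gives 4.2%, 4.5% and 4.6% for those last three. From Binomial(20) at 10% and 15%, 0 or 1 event has probability 0.39 and 0.18, and 2 or fewer 0.68 and 0.40.

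**Precision** (3 v 17 and 3 v 37, equal SD 16). Median 95% half-width: uncorrected robust 14.4 and 13.3; exact equal-variance 20.7 and 19.3; fixed-df 28.8 and 30.5 mL/min/m². Relative to the exact interval, robust is about 70% and 69% as wide, and fixed-df about 1.4 and 1.6 times as wide.

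**The case against.** The strongest reply is that the plan never says it will use an uncorrected sandwich. An analyst could use an exchangeable model-based variance with t on N−2 df, which holds exactly 5% under equal SD. In the pooled layout even the normal reference gives only about 6%. That stands. A reader might infer that the planned test has an error near 20%, or that it must be either slightly or grossly wrong. The documents support neither: they leave several options open, with errors from 5.0% to over 40% even at equal SD.

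Second, nothing in the documents says that case spread exceeds control spread. Pooling two diagnoses could make the control spread the larger, and then model-based error falls below 1%. That also stands, and is why both directions are shown. Robust error stays above 10% either way.

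Third, the correction is costly and one of several defensible choices. At 3 v 37 and equal SD, power for a 35 mL/min/m² decrease is 58%, against 94% for model-based with t on N−2 df. This stands as a cost to be declared. It does not justify leaving the choice open.

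Fourth, this is a 40-patient, single-centre observational study in which event count is the real limit. True, and no variance formula removes that. It limits the weight of the point without answering it, because the plan attaches a 0.05 level to the comparison.

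**Conclusion.** The point holds as an under-specified primary analysis in which the omission changes the result. The customary default, uncorrected robust variance with a normal reference, gives about four times the stated error: 21% at 3 v 37 and 18% at 3 v 17 with equal SD, about 12-15% at half and 22-24% at double case SD, and 11% even with 6 events. Replacing only the normal reference by t on N−2 df does not repair it. Exchangeable model-based variance is at or near nominal only under equal spread.

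The figures assume normal patient means and near-equal reading counts. The plan drops 10 minutes of VO₂ after each tube disconnect, so counts will differ; fitted GEEs with unequal counts still gave 17-18% for robust. The SD ratios other than 1 and the intraclass correlation are assumptions. Confidence is high in the omission and the robust-variance result, and lower in any single remedy being the only right one. It should be fixed before analysis.

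**What to change.** Keep the GEE comparison of window means with the patient as cluster, and write into the Data Analysis Plan:

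1. An exchangeable working correlation. Model-based variance under independence should be ruled out.
2. A small-sample-corrected variance and reference for the primary p-value and interval, in place of the uncorrected sandwich with a normal reference. One suitable choice is the Kauermann-Carroll variance with Satterthwaite df fixed from the patient counts. Another is acceptable if its error at the expected counts is shown.
3. Model-based with t on N−2 df, or a patient-level permutation test, as a labelled sensitivity analysis valid only under equal spread. At double case SD the permutation test of the mean difference has 21% error (3 v 17) and 26% (3 v 37).
4. With 0 or 1 event, the comparison is descriptive only, because the case-side variance cannot be estimated.
5. With 2 events, the corrected interval is reported, but a non-significant result is not evidence of no difference.

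**Cost.** Wording only; no new patients or data. With 3 cases and equal SD 16, power for the 53 decrease is about 90% (3 v 17) or 87% (3 v 37), against about 99.9% for the uncorrected robust test, whose power is bought with the inflated error. The interval is about 1.4-1.6 times the equal-variance width, and power for smaller decreases drops as shown above. With 2 cases, power for 53 is about 34% (2 v 18) or 31% (2 v 38), and the median half-width is about 70 or 82 mL/min/m² against a mean of 86.
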